#### 4 Study Primary and Secondary Endpoints

#### 4.1 Primary Safety Endpoint

The primary safety endpoint is a composite of Single Leaflet Device Attachment (SLDA), device embolizations, endocarditis requiring surgery, Echocardiography Core Laboratory confirmed mitral stenosis requiring surgery, LVAD implant, heart transplant, or any device related complications requiring non-elective cardiovascular surgery at 12 months.

#### 4.2 Primary Effectiveness Endpoint

The primary effectiveness endpoint is recurrent HF hospitalizations through 24 months (analyzed when the last subject completes 12 months of follow-up). For subjects who undergo MV surgery, LVAD implant or heart transplant during the follow-up, the hospitalizations for the MV surgery, LVAD or heart transplant intervention will be treated as HF hospitalizations in the analysis. For subjects in the Control group who receive the MitraClip device due to heart failure or cardiac symptoms, the hospitalizations for the MitraClip procedure will be treated as HF hospitalization in the analysis.

## 4.3 Secondary Safety Endpoints

The secondary safety endpoints are:

- A composite of all-cause death, stroke, MI, or non-elective cardiovascular surgery for device related complications in the Device group at 30 days
- All-cause mortality at 12 months

#### 4.4 Secondary Effectiveness Endpoints

The secondary effectiveness endpoints are:

- MR severity at 12 months
- Hierarchy of death and recurrent HF hospitalization (analyzed when the last subject completes 12 months of follow-up)
- Change in quality of life as measured by the Kansas City Cardiomyopathy Questionnaire (KCCQ) at 12 months from baseline
- Change in Six-Minute Walk test distance (6MWD) at 12 months from baseline
- NYHA Functional Class of I/II at 12 months
- Change in LVEDV at 12 months from baseline
- Recurrent hospitalizations all-cause (analyzed when the last subject completes 12 months of follow-up)

#### 5 Statistical Methods

#### 5.1 Randomization and Blinding

Subjects will be randomized in a 1:1 ratio to the Device or Control groups. Randomization will be stratified by site and cardiomyopathy etiology (ischemic or non-ischemic). Randomization will be performed using permuted blocks (random block sizes) and block

sizes will not be revealed to sites. The Electronic Data Capture system will be used to randomize subjects.

The subject, some site personnel and some Sponsor personnel will be aware of treatment assignment. Sponsor statisticians will not have access to any data that combines outcomes with treatment assignment prior to performing the final analysis. No Sponsor personnel will have access to outcome data summarized by treatment until the primary endpoint analysis is complete. All events constituting primary or secondary endpoints will be adjudicated by the independent Clinical Events Committee (except embolization, which will be site reported, and MV Stenosis and SLDA, which will be assessed by the Echocardiography Core Lab), along with relationship to the MitraClip device or procedure. Every effort will be made to blind the Clinical Events Committee (CEC) to the subject's treatment assignment.

#### 5.2 Data Monitoring Committee

A Data Monitoring Committee (DMC) will meet periodically at a frequency set out in the DMC charter to monitor the safety of subjects enrolled in the study. The DMC may recommend terminating the study early if there are safety concerns.

#### 5.3 Demographic and Baseline Characteristics

The Device and Control groups will be compared with respect to demographic and baseline characteristics. The two groups are expected to be well balanced at baseline due to randomization. Comparisons will be made with respect to age, sex, race and ethnicity, cardiovascular conditions, diabetes, renal disease, prior MI, prior stroke, NYHA Class, previous cardiac surgery, prior HF hospitalization, LVEF, left ventricular size, creatinine levels, STS mortality risk score, MR severity, KCCQ score, 6-minute walk distance and baseline medications. Continuous variables will be analyzed using the t-test or using non-parametric methods and categorical variables will be compared using Fisher's Exact test.

#### 5.4 Analysis Populations

The Intention to Treat, As Treated, Per Protocol and Safety Analysis populations are defined below.

#### 5.4.1 Intention to Treat (ITT) Population

The Intention to Treat population will consist of all subjects randomized in the trial. All subjects will be analyzed in the group randomized, regardless of the treatment actually received.

#### 5.4.2 As Treated (AT) Population

The As Treated population is defined as consisting of all randomized subjects according to the treatment they received. Subjects who experience a death or HF hospitalization prior to a MitraClip procedure will be considered to be in the Control group regardless of their initial

randomization. Subjects who experience a death or HF hospitalization after (but not prior to) a MitraClip procedure will be considered to be in the MitraClip group regardless of their initial randomization. For patients who do not experience a death or HF hospitalization at any time during follow-up, they will be assigned to the group that constituted > 50% of their follow-up duration. For example, if an event-free subject with 24-month follow-up received a MitraClip at 9 months, they would be assigned to the MitraClip group, whereas if an event-free subject with 24-month follow-up received a MitraClip at 15 months, they would be assigned to the Control group.

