6.7 Randomization

Before randomization:

- Echocardiography Core Lab must confirm MR severity
- Eligibility Committee must confirm that the subject is on optimal therapy including GDMT and is not appropriate for mitral valve surgery according to local site standards either at baseline or if the subject deteriorates and/or MR increases in severity during follow-up
- Site must reconfirm that subject meets eligibility criteria after Eligibility Committee approval and all baseline tests and assessments must be completed (within 14 prior to randomization)

If screening TEE shows intracardiac mass, thrombus or vegetation, or the Eligibility Committee determines subject requires additional treatment before consideration for the trial, the subject may be deferred and reconsidered for the trial, at which time the TEE must be repeated.

Subjects will be randomized or assigned as a roll-in through the eCRF database. The following baseline information must be captured for registered subjects on the appropriate eCRFs:

- Subject medical history and risk factors
- Current cardiovascular medications
- Physical measurements and vital signs (e.g. weight, height, heart rate, blood pressure and temperature)

6.8 “Treatment” Visit (Device Group or Roll-in Subjects)

For Device group or roll-in subjects, the MitraClip procedure will be performed during the “Treatment” visit. For randomized subjects, the MitraClip procedure must be completed between 1 and 14 days after randomization.

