6.8.2 MitraClip Procedure

6.8.2.1 Pre-Procedural TEE

Prior to the MitraClip procedure, Device group (after randomization) and roll-in subjects must be assessed to ensure there is no significant change in subject's overall condition (e.g., stroke, MI, active infection, endocarditis, hemodynamic instability, etc. post-randomization) that would preclude treatment. If the subject has experienced any significant change that would preclude treatment, the subject must be treated and rescheduled for the MitraClip procedure as soon as possible. Subjects are required to complete an additional transesophageal (TEE) echocardiogram study within 3 days prior to the procedure to rule out the presence of intracardiac mass, thrombus or vegetation. This echocardiogram may be performed immediately preceding initiation of the MitraClip procedure. This echocardiogram will not be submitted to the ECL. If an intracardiac mass, thrombus or vegetation or other change in echocardiographic eligibility is identified in the TEE performed immediately preceding the procedure, the subject will be considered registered even if no device implant is attempted. If a thrombus is identified, the subject should be pharmacologically treated to resolve the thrombus and, if successful, the subject should be reassessed as soon as possible to undergo the MitraClip procedure. Such subjects will be considered registered even if they do not undergo the MitraClip procedure.

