6.9.7 Procedural and Discharge Data

The following MitraClip procedural information should be recorded on the appropriate eCRF(s) after implant or attempted implant of the MitraClip device:

- General procedure information
- MitraClip implant information
- Laboratory and clinical tests
- Antiplatelet/Anticoagulation medications
- Concomitant cardiovascular medications
- Fluoroscopy duration
- Adverse events
- Protocol deviations
- Device deficiency

At the Discharge visit (Discharge occurs when subject leaves the implanting hospital), the following required tests and procedures should be completed (> 16 hours post MitraClip procedure and no later than day of discharge) as outlined below, and the information should be captured on the appropriate eCRFs:

- 12-lead ECG
- Blood draw
- Brief physical exam including vital signs (weight, heart rate, blood pressure and temperature)
- Echocardiogram (TTE) - discharge TTE must be performed at least 16 hours post MitraClip procedure and no later than 24 hours post-discharge

- Modified Rankin Scale
- Adverse events
- Protocol deviations
- Device deficiency

Instructions for the TTE are provided in this investigational plan and are located in **APPENDIX B: Echocardiography Protocol.**

6.10 “Treatment” Visit (Control Group)

The “Treatment” visit in the Control group must occur between 1 and 14 days after randomization. At the “Treatment” visit, Control group subjects will be seen by the HF specialist investigator, and will undergo a physical exam, including vital signs, cardiac health status and evaluation of heart failure medications.

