#### 5.5.1.2 As Treated (AT) Analysis

Data from all Device group subjects in the AT population will be analyzed similar to the primary analysis. For subjects who undergo other intervention for HF (e.g. MV surgery, LVAD implant or heart transplant), their follow-up information after the first intervention for HF will be excluded from the AT analysis if they have not experienced safety events prior to the date of the intervention.

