#### 5.6.1.2 As Treated Analysis

The analysis in the AT population will be identical to the ITT analysis with the exception that it will be performed in the AT population. Duration of follow-up will be calculated from the date of the randomization. For Subjects who undergo other intervention for HF (e.g. MV surgery, LVAD implant or heart transplant) in either group, their follow-up information after the first intervention for HF will be excluded from the AT analysis (regardless of treatment group).

For a sensitivity analysis, duration of follow-up will also be calculated from the date of the "Treatment" visit or the randomization date if the "Treatment" visit is missing.

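### The SAP's As Treated rule groups subjects by whether their first death or HF hospitalization came before the clip, so the comparison leans toward the Device even when there is no effect

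*SAP*

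**What the plan says.** SAP 5.4.2 opens by defining the AT population by treatment received, then gives three rules that depend on outcome:

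- "Subjects who experience a death or HF hospitalization prior to a MitraClip procedure will be considered to be in the Control group", regardless of randomized arm.
- Subjects whose first such event follows the procedure count as MitraClip.
- For subjects with no event, "they will be assigned to the group that constituted > 50% of their follow-up duration".

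For the primary effectiveness endpoint, SAP 5.6.1.2 states: "Duration of follow-up will be calculated from the date of the randomization". A sensitivity analysis restarts the clock at the Treatment visit. For randomized Device subjects, Protocol 6.8 requires that "the MitraClip procedure must be completed between 1 and 14 days after randomization". Protocol 6.8.2.1 lets the procedure be rescheduled if the subject's condition changes, and says of those with a thrombus on the pre-procedure TEE: "Such subjects will be considered registered even if they do not undergo the MitraClip procedure". Control subjects may not be clipped before the 24-month visit (SAP 3).

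AT analyses are planned for primary safety (SAP 5.5.1.2), primary effectiveness (5.6.1.2), mortality (5.5.2.2.1) and every secondary effectiveness endpoint (5.6.2). Protocol 7.1.3 defines AT differently: subjects treated as randomized, Device refusers excluded, data after a Control clip dropped, and no sorting by event.

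**The concern.** Grouping on the order of event and clip uses the outcome to define exposure. Almost all planned reclassification runs one way, because only Device subjects are meant to have a clip within 24 months. Two things follow:

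- The event-free wait of every Device subject who stays in the group counts as MitraClip time, although no clip was in place.
- Device subjects with an early event, who tend to be the frailer ones, carry their whole follow-up and later events into Control, even if they are clipped a few days later.

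Both favour the Device. An AT analysis is read as a check on ITT, and a check that leans toward the Device under the null cannot do that job. Treated subjects are also lost from the AT safety analysis, which reads: "Data from all Device group subjects in the AT population will be analyzed similar to the primary analysis".

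**Working it through.** **Inputs.** From SAP 5.8.2: 610 subjects (305 per arm), one-sided 5%, 0.6 HF hospitalizations per year in Control and 0.42 in Device, 12-month mortality 27% and 22%, attrition 7.5%, gamma frailty with variance 1 and exponent 1, follow-up 12 to 24 months. For the null, both arms get 0.6 and 27%. Assumed, because the documents do not give them: constant hazards; 60% of subjects followed for 24 months and the rest uniform over 12 to 24; waits uniform over days 1 to 14, with fixed days as the range; no crossover; every Device subject clipped unless dead or withdrawn first.

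**Step 1: the plan's own figure.** A joint frailty model fitted to data simulated from the SAP's design values gives ITT power of 79.5%, against the stated figure of about 80%.

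**Step 2: how many subjects move.** Under this frailty, 12-month survival is 1/(1+h), so h = 1/0.73 − 1 = 0.370 per year. The combined rate is 0.6 + 0.370 = 0.970, and P(event by t) = 1 − 1/(1 + 0.970t).

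- Mean wait 7.5 days: 0.970 × 7.5/365 = 0.0199, P = 0.0195, × 305 ≈ 6.0 subjects.
- Wait 14 days: 0.970 × 14/365 = 0.0372, P = 0.0359, × 305 ≈ 10.9 subjects.

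The more-than-50% rule also sends to Control any event-free Device subject who withdraws before twice the wait. The withdrawal rate is −ln(0.925) = 0.078 per year, so this adds 305 × 0.078 × 15/365 ≈ 1.0, or 305 × 0.078 × 28/365 ≈ 1.8 at day 14. The simulated totals are 6.9 and 12.7.

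Of the 6.9, about 6.0 × 0.6/0.970 = 3.7 had an HF hospitalization as first event and go on to the clip, and about half of the 1.0 are clipped and then withdraw. The simulated number clipped is 4.1.

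**Step 3: no true effect** (8,000 trials per row; Monte Carlo SE 0.2 to 0.5 points).

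| Analysis and timing | HR | One-sided rejection |
|---|---|---|
| ITT | 1.00 | 5.6% |
| PP | 1.00 | 5.5% |
| AT, all on day 1 | 0.99 | 6.1% |
| AT, all on day 7 | 0.92 | 15.1% |
| AT, uniform days 1–14 | 0.92 | 15.6% |
| AT, all on day 14 | 0.85 | 31.3% |
| AT, Treatment-visit clock, uniform | 0.96 | 9.1% |
| AT, Treatment-visit clock, day 14 | 0.92 | 14.1% |

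Separately written code with other accrual assumptions gives 0.917 and 15.3% for the uniform wait, 0.851 and 31.1% for day 14, and 0.999 and 4.8% for a wait of zero. The wait is therefore the source. The Treatment-visit clock helps only in part, because grouping is still by outcome.

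**Step 4: other assumptions** (uniform wait).

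- Event rates in the first 30 days half or double the later rates: 0.95 and 9.6%, or 0.85 and 32%.
- Truncation at MV surgery, LVAD or transplant (SAP 5.6.1.2) at an assumed 1–3% per year: 0.91 and 16%.
- Frailty variance 0.5, or near zero: 0.946 and 12.0%, or 0.969 and 8.9%.
- SAP design effect: ITT relative risk reduction 30%, AT 34%.

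**Step 5: other endpoints under the null.** The AT 12-month mortality HR is 0.93 (0.99 at day 1, 0.87 at day 14). Finkelstein-Schoenfeld on AT groups gives false Device wins in 8.5% of trials against a nominal 2.5% (2.9% at day 1, 20.3% at day 14).

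**Step 6: the replacement.** With the clip as a time-dependent exposure, HR is 1.00 and rejection 5.0–5.5% under constant rates. With half or double early rates it is 1.00 and 5.0–5.8% if the baseline hazard may vary over time, but 1.04 or 0.92 if it is held constant. For Finkelstein-Schoenfeld, Protocol 7.1.3 alone gives 3.7% false Device wins (4.9% at day 14), because it drops Device deaths during the wait and keeps Control ones. Requiring the Treatment visit in both arms and starting time there gives 2.5%.

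**The case against.** No decision rests on AT. Effectiveness is decided by ITT (SAP 5.6.1), primary safety by the Safety Analysis population (5.5.1.1), and multiplicity control covers ITT only (5.9). PP is planned and is neutral here. The documents give a window for the wait, not a distribution, so 15.6% is one point in a range. All of this stands. It limits the severity and means the direction is firmer than the size.

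The replacement is also not neutral if sicker Device subjects go unclipped. With 2% or 5% unclipped in proportion to frailty (assumed), the time-dependent analysis gives 0.96 and 8.8%, or 0.91 and 16.1%. PP does better (0.98 and 7.2%, or 0.95 and 9.8%), while the SAP rule does worse than either (0.88 and 22.9%, or 0.84 and 34.1%). This too stands, and the SAP should say so.

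One could count only about 6 moved subjects, or about 11 at day 14. That count covers early events and leaves out the event-free early withdrawals that the more-than-50% rule sends to Control.

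On safety, the Device group in SAP 5.5.1.2 could mean the randomized arm. The SAP should say which is meant. No error rates were computed for MR severity, KCCQ, 6MWD, LVEDV, NYHA or all-cause hospitalization.

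**Conclusion.** The concern holds. Under no effect the SAP's AT rule favours the Device at every wait above zero. Within the planned window the HF hospitalization HR falls to between 0.99 and 0.85 and one-sided rejection rises to between 6.1% and 31.3%. The even-spread case is 0.92 and 15.6%, close to three times the ITT rate. These sizes rest on the SAP 5.8.2 inputs, constant hazards except where varied, and the assumed waits. No further bias from Control crossover is claimed, because that depends on how crossover arises. Trial success is not at risk. What is lost is the value of AT as support for ITT on effectiveness and mortality. The conflict with Protocol 7.1.3 needs resolving whatever the size of the bias. This should be fixed before AT results are reported.

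**What to change.** Delete the three outcome-based rules in SAP 5.4.2 and replace them as follows.

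1. For recurrent HF hospitalization, recurrent all-cause hospitalization and mortality, AT analyses include all randomized subjects. MitraClip is a time-dependent exposure: 0 from randomization until the first procedure, 1 from the procedure day onward. Events and person-time count in the state in which they occur. The baseline hazard may vary over time.
2. For endpoints that need one group per subject (primary safety, MR severity, KCCQ, 6MWD, LVEDV, NYHA, Finkelstein-Schoenfeld), AT uses the Protocol 7.1.3 definition: subjects treated as randomized, analysed in that group, with data after a Control clip excluded. In both arms only subjects who reach the Treatment visit are included, and Finkelstein-Schoenfeld time starts at that visit. No subject is assigned by event status.
3. Reconcile SAP 5.4.2 with Protocol 7.1.3. State that both AT analyses remain open to selection if not receiving the clip is related to prognosis, so ITT stays primary.

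The cost is SAP wording and a little programming, mainly a time-varying exposure in the joint frailty model. All dates are already collected. The AT estimate becomes slightly less favourable to the Device, and AT then carries two definitions, one for time-to-event endpoints and one for the rest.

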#### 5.4.3 Per Protocol (PP) Population

The Per Protocol population is defined as consisting of all randomized subjects who meet all major study inclusion criteria and none of the major exclusion criteria for the trial, are treated according to the randomized assignment, and followed consistent with all major study processes. Subjects who do not complete the "Treatment" visit will be excluded from the PP population. Subjects who are randomized to the Device group but do not have a MitraClip procedure attempted between 1-14 days of the randomization will be excluded from the PP population. For subjects in the Control group who receive the MitraClip device, follow-up data after the date of the procedure will be excluded from analysis. For subjects in either group who undergo other major intervention for HF (e.g. MV surgery, LVAD implant or heart transplant), follow-up data after the date of the intervention will be excluded from analysis.

## 5.4.4 Safety Analysis (SA) Population

The Safety Analysis population is defined to consist of randomized Device group subjects in whom a MitraClip procedure is attempted.

#### 5.5 Analysis of Safety

#### 5.5.1 Primary Safety Endpoint

A composite of device related complications including Single Leaflet Device Attachment (SLDA), device embolizations, endocarditis requiring surgery, Echocardiography Core Laboratory confirmed mitral stenosis requiring surgery, LVAD implant, heart transplant, or any device related complications requiring non-elective cardiovascular surgery at 12 months will be the primary measure of safety.

All events constituting the primary safety endpoint will be adjudicated by the independent Clinical Events Committee (except embolization, which will be site reported, and Mitral Valve Stenosis and SLDA, which will be assessed by the Echocardiography Core Lab). SLDA is defined as unilateral MitraClip detachment from one leaflet, as assessed by the Echocardiography Core Laboratory as definite. In the case of MV surgery, SLDA can also be identified by operating physician.

The analysis of the primary safety endpoint is a test of the proportion of subjects free from the composite of safety events in the Device group at 12 months to a pre-specified performance goal of 88%.

#### **Hypothesis:**

The null and alternative hypotheses may be stated as:

$$H_0$$
:  $P_D(12) \le 0.88$  vs.

$$H_1$$
:  $P_D(12) > 0.88$ 

where,  $P_D(12)$  is the proportion of subjects free from safety events at 12 months in the Device group. This endpoint will be evaluated at the one-sided significance level of 5%.

Since this is a 12-month endpoint, all data will be truncated at 12 months for the analysis. The Kaplan Meier survival estimate, together with variance estimated by the Greenwood method, will be used to set up the test of the null hypothesis as a Z-test. The null hypothesis will be rejected at the 5% level of significance if the test statistic is greater than 1.645.

The test statistic is:

$$\frac{\hat{P}_{D} - 0.88}{\sqrt{\hat{V}(\hat{P}_{D})}}$$

where  $\hat{P}_D$  is the Kaplan Meier survival estimate in the Device group.  $\hat{V}(\hat{P}_D)$  is the Greenwood estimate of the variance.

The primary safety endpoint will be considered met if the null hypothesis is rejected at the 5% level of significance in the primary analysis described below. Sensitivity analyses will also be performed in addition to the primary analysis as detailed below.

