7.2 Primary Endpoints

7.2.1 Primary Safety Endpoint

A composite of Single Leaflet Device Attachment (SLDA), device embolizations, endocarditis requiring surgery, Echocardiography Core Laboratory confirmed mitral stenosis requiring surgery, LVAD implant, heart transplant, and any device related complications requiring non-elective cardiovascular surgery will be the primary measure of safety. The analysis of the primary safety endpoint is a comparison of the freedom from the composite of Device related safety events in the Device group at 12 months to a pre-specified performance goal of 88%.

Hypothesis:

The null and alternative hypotheses are stated as:

$$H_0: P_D(12) \leq 88\% \text{ vs.}$$

$$H_1: P_D(12) > 88\%$$

where $P_D(12)$ is freedom from the primary safety composite in the Device group at 12 months. A one-sided Z-test will be performed to test the null hypothesis against the alternative hypothesis. Kaplan-Meier survival estimate at 12 months, together with the variance estimated using the Greenwood formula, will be used to calculate the Z-statistic. The null hypothesis will be rejected at the 5% significance level if the Z-statistic is greater than 1.645.

Analysis:

Since the primary safety endpoint will be evaluated at 12 months, all data will be truncated at 12 months for the analysis. The Kaplan Meier survival estimate, together with variance estimated by the Greenwood method¹⁷ will be used to set up the test of the null hypothesis as a Z-test. The null hypothesis will be rejected at the 5% level of significance if the test statistic is greater than 1.645.

The primary analysis will be performed in all Device group subjects in whom a MitraClip procedure is attempted. Additional analyses, including sensitivity analyses, are detailed in the **Statistical Analysis Plan**.

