#### 5.5.1.4 Tipping-point Analysis

Tipping point analysis on the primary safety endpoint at 12 months will be conducted as a sensitivity analysis. Subjects in the Safety Analysis population who withdraw from the study before completing a year of follow-up will be analyzed one at a time as having experienced a primary safety endpoint event on the date of withdrawal. In addition, patients with unevaluable echocardiograms at last follow-up will be analyzed one at a time as having experienced a primary safety endpoint event on the date that follow-up occurred.

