#### 5.5.2 Secondary Safety Endpoints

#### 5.5.2.1 Composite 30-Day Secondary Safety Endpoint

A composite of all-cause death, stroke, MI, or non-elective (urgent or emergent) cardiovascular surgery for device related complications in the Safety Analysis Population at 30 days will be used as a secondary measure of safety. The analysis of the secondary safety endpoint is a one-group test against a performance goal for the proportion of subjects in the Safety Analysis Population free from the composite of secondary safety events at 30 days. The null and alternative hypotheses may be stated as:

$$H_0$$
:  $P_D(30) \le 0.80 \text{ vs.}$ 

$$H_1: P_D(30) > 0.80$$

where, PD(30) is the proportion of subjects free from composite of secondary safety events at 30 days in the Safety Analysis Population. This endpoint will be evaluated at the one-sided significance level of 5% with an exact test for a single proportion. The denominator of the proportion will exclude subjects in the Safety Analysis Population who terminated from the study prior to the lower window of the 30-Day visit (Day 27) without any site reported adverse events.

Components of the secondary composite safety endpoint will be summarized and reported for the Device group.

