#### 5.8.1 Primary Safety Endpoint

**Table 1** lists the event rates assumed for the components of the composite primary safety endpoint in the Device group

EventDevice GroupSLDA4%Embolization<0.1%	Endocarditis<0.1%	Mitral Stenosis Confirmed by ECL
That Requires Surgery<0.1%	LVAD Implant, Heart Transplant1%Other Device-related Complications<0.1%	Table 1: Assumptions for Primary Safety Event Rates at 12 Months

Two thousand (2000) simulations were performed to calculate sample size and power for the primary safety endpoint. Assuming 22% mortality and 7.5% attrition at 12 months, a total of 305 subjects in the Device group will provide > 95% power to reject the null hypothesis at the one-sided significance level of 5%.

~6%

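### The primary safety test is labelled one-sided 5% but rejects about 7% of the time at the 88% goal under the plan's own assumptions; a log(-log) version brings it to about 5% or below for 1 to 3 points of power

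*SAP*

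**What the plan says.** SAP 5.5.1 (Hypothesis) sets H0: P ≤ 0.88 against H1: P > 0.88 for 12-month freedom from the composite. On method it says: "The Kaplan Meier survival estimate, together with variance estimated by the Greenwood method, will be used to set up the test of the null hypothesis". The statistic is (KM − 0.88) divided by the square root of the Greenwood variance, with no transformation. On the level it says "This endpoint will be evaluated at the one-sided significance level of 5"%, and "The null hypothesis will be rejected at the 5% level of significance if the test statistic is greater than 1.645". Protocol 7.2.1 agrees: "The null hypothesis will be rejected at the 5% significance level if the Z-statistic is greater than 1.645".

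The decision rests on this test alone: "The primary safety endpoint will be considered met if the null hypothesis is rejected at the 5% level of significance in the primary analysis". The As Treated and Per Protocol analyses (SAP 5.5.1.2 and 5.5.1.3) are run in the same way as the primary analysis. SAP 5.5.1.4 adds: "Tipping point analysis on the primary safety endpoint at 12 months will be conducted as a sensitivity analysis".

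On sample size, SAP 5.8.1 says: "Assuming 22% mortality and 7.5% attrition at 12 months, a total of 305 subjects in the Device group will provide > 95% power". Its Table 1 puts the total event rate at about 6%. The SAP reports no rejection rate at the 88% boundary. The other endpoint tested against a performance goal, the 30-day composite in SAP 5.5.2.1, is assessed "with an exact test for a single proportion".

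**The concern.** A Wald test on the plain scale uses the standard error at the estimate. For a proportion near 1, that standard error shrinks as the estimate rises. Any estimate high enough to look favourable is therefore judged against a smaller error than applies at 88%, and the test rejects too often at the boundary. With roughly 30 to 35 events expected under the null, the sample is not large enough for this to wash out.

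Safety is a co-primary endpoint. Both co-primaries must be met for trial success, and together they gate every secondary claim (SAP 5.9 and 5.10). The safety comparison is single-arm, so the level of this one test is what limits the chance of passing a device that sits exactly at the goal. At 7%, that chance is about 1 in 14 (1/0.07), against the stated 1 in 20.

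**Working it through.** **Inputs.** From SAP 5.5.1: goal 0.88, cutoff 1.645, one-sided, truncation at 12 months. From SAP 5.8.1: n = 305, 22% mortality, 7.5% attrition, event rate about 6%, power >95%. Assumptions made here: event timing (not given in the SAP), independent exponential death and withdrawal censoring, events dated when they occur, and n = 290 as a second size. The last allows for 15 randomized Device subjects with no attempted procedure, whom SAP 5.4.4 excludes.

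**1. The plan's power figure.** Simulating the stated test at a 6% event rate with n = 305 gives 96.6-98.5%, depending on event timing. The stated >95% is reproduced, so the simulated test matches the plan.

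**2. Hand check without censoring, n = 305.** Here KM = 1 − x/n and the Greenwood variance is KM(1 − KM)/n.

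- x = 28: KM = 277/305 = 0.9082; SE = √(0.9082 × 0.0918/305) = 0.01653; Z = 0.0282/0.01653 = 1.705, so it passes.
- x = 29: KM = 0.9049; SE = 0.01680; Z = 1.48, so it fails.
- The stated rule is therefore to pass with 28 or fewer events. For X ~ Bin(305, 0.12), P(X ≤ 28) = 7.30%.
- Mechanism: the SE at 0.88 is √(0.88 × 0.12/305) = 0.01861. On that SE the cutoff would be 0.88 + 1.645 × 0.01861 = 0.9106, which 28 events (0.9082) does not reach.

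**3. The log(-log) test on the same data.** Z = [ln(−ln 0.88) − ln(−ln KM)] / {√(Σ d/[r(r − d)]) / |ln KM|}, where d is events and r the number at risk. Without censoring the sum is (1 − KM)/(n·KM).

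- x = 28: ln(−ln 0.88) = −2.0570 and ln(−ln 0.9082) = −2.3404, a difference of 0.2833; SE = 0.01820/0.0963 = 0.1891; Z = 1.499, so it fails.
- x = 27: Z = 1.670, so it passes. P(X ≤ 27) = 5.01%.
- At n = 290 the stated rule passes with ≤26 events (6.26%) and log(-log) with ≤25 (4.19%).
- At other sizes the uncensored log(-log) level reaches 5.28% (n = 275), 5.19% (n = 285) and 5.10% (n = 295). This is discreteness.

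**4. Level with the planned censoring.** True freedom 88%, 60,000 simulations per cell, Monte Carlo SE about 0.1 point.

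| Event timing | n = 305 stated | n = 305 log(-log) | n = 290 stated | n = 290 log(-log) |
|---|---|---|---|---|
| Constant hazard | 6.85% | 4.27% | 6.99% | 4.23% |
| 50% of hazard in first 30 days | 7.18% | 4.60% | 6.79% | 4.31% |
| 80% of hazard in first 30 days | 6.87% | 4.38% | 7.06% | 4.51% |
| All in months 6-12 | 7.02% | 4.25% | 7.17% | 4.31% |

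A repeat of the first three timings at n = 305 with 200,000 simulations gave 6.98%, 6.92% and 6.82% for the stated test, and 4.42%, 4.33% and 4.38% for log(-log).

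**5. Power at the planned 6%.** 20,000 simulations per cell, Monte Carlo SE about 0.1-0.2 point.

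| Event timing | n = 305 stated | n = 305 log(-log) | n = 290 stated | n = 290 log(-log) |
|---|---|---|---|---|
| Constant hazard | 97.5% | 95.6% | 97.0% | 94.6% |
| 50% of hazard in first 30 days | 98.1% | 96.6% | 97.6% | 95.8% |
| 80% of hazard in first 30 days | 98.5% | 97.3% | 98.2% | 96.7% |
| All in months 6-12 | 96.6% | 94.1% | 96.1% | 93.1% |

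The loss is 1.2-2.5 points at n = 305 and 1.5-3.0 points at n = 290. The components in Table 1 add to 5.0-5.4% (4 + 1 + four entries below 0.1). At 5.4% with constant hazard and n = 305, power is 99.2% against 98.4%, a loss of under 1 point.

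**The case against.** **Nothing is miscalculated.** The value 1.645 is the right one-sided quantile, KM with Greenwood variance is a standard large-sample test, and the power claim reproduces. That stands: this is a choice of method, and a reader should not infer a wrong critical value or a false power figure. It does not rescue the statement of the level, which is wrong at this sample size.

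**The consequence is small.** The two rules part at a KM of about 0.908-0.916, against a planned 0.94. Trial success also needs effectiveness, powered at about 80%. If the endpoints are independent, a device at exactly 88% with the planned benefit succeeds about 0.07 × 0.80 = 5.6% of the time. This also stands. A reader might take 1 in 14 as the trial's false-success rate, but it describes the safety test alone.

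**The exact test for the 30-day composite proves little.** That endpoint is a simple proportion with its own denominator rule. The 12-month endpoint has deaths and withdrawals to censor, so a single-proportion exact test does not carry over. The contrast does not show that the authors saw the problem and left it.

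**The simulations date events when they happen.** Single leaflet attachment is 4 of the roughly 6 points and is read by the echo core laboratory, so detection may follow the visit schedule. The documents give no rule for dating these events. A dating convention could bias KM under either test, so the levels shown are conditional on exact dating. This limits the claim for the fix but does not defend the stated test.

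**The tipping-point analysis may expose a fragile result.** It may, but it reassigns outcomes and leaves the level as it is, and the endpoint is decided on the primary analysis.

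**Conclusion.** The point holds. Under the SAP's own inputs, the co-primary safety test has a true one-sided level of about 7% (6.8-7.2% across four event timings, at n = 305 and at an assumed n = 290), where the plan states 5%. The result barely moves with event timing. It rests on independent censoring and on events being dated when they occur.

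A tempting stronger reading is that log(-log) keeps the level below 5% in every setting. The figures do not support that. With the planned censoring it is 4.2-4.6%; with none it is 5.01% at n = 305 and up to about 5.3% at other sizes. The defensible claim is approximately 5% or below. Since only a result within about one event of the boundary would change, the plan should be corrected, but the trial's conclusions are unlikely to turn on it.

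**What to change.** In SAP 5.5.1 and protocol 7.2.1, keep the KM estimate, the Greenwood sum and the 1.645 cutoff, and test on the log(-log) scale: reject if [ln(−ln 0.88) − ln(−ln KM)] / {√(Σ d/[r(r − d)]) / |ln KM|} > 1.645. A logit version would also serve: its simulated level is 4.4-4.8%, with power within 0.3 point at 6%. Arcsine would not (5.7-6.0%).

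In SAP 5.8.1, replace >95% with about 95% for the revised test, noting a range of about 94-97% at n = 305 and 93-97% with 290 attempted procedures, depending on event timing. State the rejection rate at 88% beside it.

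The cost is 1 to 3 points of power at the planned rate, and >95% is no longer met in three of the eight settings run (94.1%, 94.6% and 93.1%). The protocol wording also needs an amendment with IRB/EC approval under protocol 12.1, at up to 100 sites. Both changes should be fixed before safety outcomes are analysed.
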